3. End of Treatment (EOT) for patients who complete the treatment and withdrawal/taper periods will be completed at Visit 19. Patients who discontinue study drug prematurely should ideally be observed until study end as if they were still receiving blinded study treatment. There are 4 options for observing patients after premature drug discontinuation. Sections [3.3.4.1](#) and [6.2.2](#) and [6.2.2.1](#) provide additional information.  
Early Discontinuation (D/C) Option 1: An EOT Visit must be conducted within 7 days of the last dose of study medication for patients who agree to conduct regularly scheduled visits after premature drug discontinuation. Thereafter, patients should be followed up according to the regular visit schedule. Visit 16 will be the final visit for patients choosing this Early D/C Option.  
Early D/C Options 2-4: An EOT Visit must be conducted within 7 days of the last dose of study medication for patients who agree to conduct the remaining visits over the phone, or patients who agree to be contacted or data collected via alternative sources approximately 28 weeks after the patient was randomised.
4. Patients who complete the treatment and withdrawal/taper periods will be scheduled for a Follow-Up Visit 28 days after Visit 16. Patients who enter the withdrawal/taper period, but discontinue taking their study drug will have a Follow-up Visit as planned at Week 32.
5. Patients who prematurely discontinue study medication and choose Early D/C Option 1 do not need a Follow-Up Visit if they discontinued >4 weeks prior to Visit 16. If a patient choosing Early D/C Option 1 discontinues <4 weeks prior to Visit 16, a Follow-up Visit will be performed 28 days after the EOT Visit. Patients who prematurely discontinue study medication and choose Early D/C Options 2-4 will have a Follow-Up Visit performed 28 days after the EOT visit. See Sections [3.3.4.1](#), [6.2.2](#), and [6.2.2.1](#).
6. Written informed consents for main study and optional pharmacogenomics test for deoxyribonucleic acid (DNA) banking must be obtained before any study-related procedures and assessments are performed. The registration of patients for the study is through the Interactive Response Technology (IRT). Re-consenting may become necessary when new relevant information becomes available and should be conducted according to the sponsor's and Institutional Review Board (IRB)/ Independent Ethics Committee's (IEC) instructions.

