17. Patients who have prematurely discontinued study drug and have not continued making regular visits (in person or phone) must have Vital Status collected approximately 28 weeks after the patient was randomised.

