### 7.3 PLANNED ANALYSES

Two patient populations are defined:

- The treated set (TS) includes all patients who were dispensed study medication and were documented to have taken at least one dose of investigational treatment
- The full analysis set (FAS) includes all patients in the treated set with at least one post-baseline measurement of any type

No per protocol population will be used for analyses; however protocol violations will be identified and listed.

Analysis sets will be fully defined in TSAP.

Three analysis periods are defined:

- **Intent to Treat (ITT) follow-up:** from treatment start date until the end of the intended complete treatment period:

For patients who complete the trial according to the [flow chart](#), the withdrawal/taper period is not included. Additionally, if a patient happens to take drug for 29 weeks (i.e. 1 week longer than the planned 28 weeks) and then begin the withdrawal/taper period, the withdrawal/taper period will not be included.

For patients who discontinue prior to the 28 week treatment period, e.g. at week 25, the follow-up period until the end of week 28, is included.

- **Full follow-up:** from randomisation until the end of the trial, including all observed time on and off trial medication until the follow-up visit or the last date of contact:

For patients who discontinue trial medication according to the [flow chart](#), the withdrawal/taper period is included. Additionally, if a patient happens to take drug for 29 weeks (i.e. 1 week longer than the planned 28 weeks) and then begin the withdrawal/taper period, the withdrawal/taper period is included.

For patients who discontinue prior to the 28 week treatment period, e.g. at week 25, the follow-up period until the last contact date is included.

The full follow-up analysis period will be used as a sensitivity analysis to the ITT follow-up analysis.

- **On-treatment:** from treatment start date until the date of discontinuation of trial medication + 7 days:

For all patients this analysis period includes only the time on trial medication + 7 days after taken off trial medication.

For patients randomised to the withdrawal period, this will include 28 weeks of treatment, or for early discontinued patients, the time period on active treatment prior to discontinuation + 7 days, which corresponds to the 7 days abrupt withdrawal period.

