4. CHANGES IN THE PLANNED ANALYSIS OF THE STUDY

CTP section 7.5 specifies: All patients will be followed up for relapse [...]. Any patient who has not relapsed will be censored in the analysis of the primary endpoint at the time of last patient contact. In fact, the primary endpoint analysis is the ITT analysis, which is indicated in CTP section 7.3 to include relapses only during the 28-week planned on-treatment period. See Section 6.6 for corrections.

The following additional analyses, which were not mentioned in the CTP, were added:

- Time to Discontinuation was added as a further endpoint.
- Time to Treatment Discontinuation or Relapse was added as a sensitivity analysis to the primary endpoint

Recruitment to this study was stopped early by the Sponsor due to slow enrolment. As a result, statistical power is reduced because of sample size reduction, analyses remain the same as planned, see more details in Section 7.4. A fast-track approach will be taken in order to expedite decision making and for preparation of the planned phase III trials, see more details in Section 9.2.

Details surrounding the planned assessment of the impact of the COVID-19 pandemic on the trial, are specified in section 9.3.

Hazard ratio calculated from the Cox proportional hazard model and a 95% confidence interval around the HR will be provided for primary and secondary endpoint; relative risk reduction and a 95% confidence interval around the RRR will be provided for further endpoints.

Due to the fact that there were cases where the site was not able to enter the data into the iPad in a timely manner and was unable to confirm with the site the actual date the assessment was completed, visit start date as recorded on the CRF will be used as the analysis date. Confirmed that all assessments started on the visit date and therefore it is a reasonable assumption to use the CRF recorded visit date as the analysis date.

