6. GENERAL ANALYSIS DEFINITIONS

6.1 TREATMENT(S)

As described in Section 3 of the revised CTP, patients will be randomized in equal allocation to one of three treatment dosage groups (50 mg, 25 mg and placebo) for analysis purposes.

For randomization purposes 6 arms have been defined:

- BI 409306 50 mg q.d for 28 weeks and 7 days of withdrawal from treatment
- BI 409306 50 mg q.d for 28 weeks and 7 days of tapering from treatment
- BI 409306 25 mg q.d for 28 weeks and 7 days of withdrawal from treatment
- BI 409306 25 mg q.d for 28 weeks and 7 days of tapering from treatment
- Placebo for 28 weeks and 7 days of withdrawal from treatment
- Placebo for 28 weeks and 7 days of tapering from treatment

Table 6.1: 1 Treatments and their labels per randomization list

Treatment	Short label
BI 409306 50 mg q.d. taper	BI 409306 50 mg taper
BI 409306 50 mg q.d. withdraw	BI 409306 50 mg withdraw
BI 409306 25 mg q.d. taper	BI 409306 25 mg taper
BI 409306 25 mg q.d. withdraw	BI 409306 25 mg withdraw
Placebo taper	Placebo taper
Placebo withdraw	Placebo withdraw

The treatment period is defined as 28 weeks, hence for most analyses the taper/withdrawal period will not be considered and the arms corresponding to the same doses of treatment will be pooled, resulting in the following treatment labels for displays.

Table 6.1: 2 Treatments and their labels in specified analyses

Treatment (per rand list)	Short label (in displays)	
BI 409306 50 mg q.d. taper	DI 400206 50 mg	
BI 409306 50 mg q.d. withdraw	BI 409306 50 mg	
BI 409306 25 mg q.d. taper	DI 400206 25 ~	
BI 409306 25 mg q.d. withdraw	BI 409306 25 mg	

Proprietary confidential information © 2021 Boehringer Ingelheim International GmbH or one or more of its affiliated companies

Treatment (per rand list)	Short label (in displays)
Placebo taper	Placebo
Placebo withdraw	Piacedo

The trial consists of a 28 day screening period, followed by a 28 week treatment period (after randomization), followed by a 7 day taper/withdraw (T/W) period and a 21day follow-up.

For analysis purposes three periods have been defined in section 7.3.1 of the CTP:

• Intent to Treat (ITT) follow-up

This is the intended 28 week treatment period. It does not include the T/W period. For patients who discontinue early, their follow-up information until the end of the planned 28 week treatment period is included.

• Full follow-up

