6.6 HANDLING OF MISSING DATA AND OUTLIERS

Assessment of relapse data (primary endpoint):

All patients will be followed up for relapse [...]. Any patient who has not relapsed will be censored in the analysis of the primary endpoint at the time of their planned complete 28-week treatment period. This does not include the T/W period. For AEs that meet the primary endpoint criteria, missing or incomplete AE dates are imputed according to BI standards.

The sensitivity analysis will use the Full Follow-up period to demonstrate the robustness of the results of the main analysis. See revised CTP Section 7.3

PANSS positive symptoms (key secondary analysis)

Change from baseline in PANSS positive symptoms will be evaluated using Mixed effect Model for Repeated Measures (MMRM) approach. This approach allows for missing data, assuming they are missing at random. All patients can be included in the model and missed visits will not be imputed. If a PANSS item is missing, the missing score on that individual PANSS item will not be imputed; if individual PANSS item is missing within a PANSS subscale, this subscale cannot be included in the calculation of the overall PANSS total score. Therefore, patients with missing individual PANSS items will also have a missing PANSS total score at that visit. However, subscale scores will be used for analysis if none of the individual items are missing.

Relative Risk Reduction (RRR)

Per revised CTP Section 7.5.:

All patients in the FAS will be included [...] *regardless of drop-out.*

For

AE dates

Missing or incomplete AE dates are imputed according to BI standards (see "Handling of missing and incomplete AE dates") (3).

PK data

Missing data and outliers of PK data are handled according to Reference (2) and as described in Section 10 of the revised CTP.

In December 2019, during the conduct of the trial, a Visit 8 eCRF page was added to capture
the date and time of the last dose of BI drug intake before the PK sampling performed at Visit
8. For patients who had completed the trial at that time, or patients for whom the visit 8 date
had passed, the data will be used to inform the date and time of the last BI drug
intake.
Sensitivity analysis: the date and time of the last dose of BI drug intake at Visit 8 collected in
the eCRF will be compared to the information recorded in This will be done for

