- Patients with event counted: <date of event> <date of first drug administration> +1 day
- Patients without event counted: <date of last dose of study drug or date of Visit 16> <date of first drug administration >+1 day
- B. Patients completing treatment period and study period (for Full FU analysis): Events (relapses) are counted in the FU time to event analysis whenever they occur between the first dose of randomized treatment and the patient's EOS date.
 - Patients with event counted: <date of event> <date of first drug administration> +1 day

- Patients without event counted: <date of EOS> <date of first drug administration
- C. Patients who chose Early Discontinuation Option 1 or Option 2 per CTP (ITT and Full FU analysis):
- And completed required study period: Events (relapses) are counted in the time to event analysis whenever they occur between the first dose of randomized treatment and the patient's EOS date.
 - Patients with event counted: <date of event> <date of first drug administration> +1
 - Patients without event counted: <date of EOS> <date of first drug administration >+1 day
- And discontinued or did not complete required study period: Events (relapses) are counted in the time to event analysis whenever they occur between the first dose of randomized treatment and the patient's last at-risk date.
 - Patients with event counted: <date of event> <date of first drug administration> +1 day
 - Patients without event counted: <date of last at-risk date > <date of first drug administration >+1 day
- Patients who chose Early Discontinuation Option 3 or Option 4 per CTP (ITT and D. Full FU analysis):
- And completed required study period: Events (relapses) are counted in the time to event analysis whenever they occur between the first dose of randomized treatment and the patient's End of Study Date.
 - Patients with event counted: <date of event> <date of first drug administration> +1
 - Patients without event counted: < date of EOS > < date of first drug administration >+1 day
- And discontinued or did not complete required study period: Events (relapses) are counted in the time to event analysis whenever they occur between the first dose of randomized treatment and the date of last at-risk date.
 - Patients with event counted: <date of event> <date of first drug administration> +1
 - Patients without event counted: < date of last at-risk date > < date of first drug administration >+1 day

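### SAP 7.4.1 rules C and D run the primary ITT analysis to end of study for early discontinuers, past the 28-week limit set elsewhere in the plan

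*SAP*

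**What the plan says.** Four places end the primary ITT period at week 28.

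- Protocol 7.3 gives a worked case for a patient who stops early: "e.g. at week 25, the follow-up period until the end of week 28, is included". It reserves the last contact date for the Full follow-up period.
- SAP 4, as a correction to protocol 7.5, says the primary analysis is "to include relapses only during the 28-week planned on-treatment period".
- SAP 6.1: "For patients who discontinue early, their follow-up information until the end of the planned 28 week treatment period is included".
- SAP 6.6: a patient without relapse "will be censored in the analysis of the primary endpoint at the time of their planned complete 28-week treatment period".

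SAP 7.4.1 then gives the date formulas. Completers get two rules: A for ITT (Visit 16, or last dose if later) and B for Full follow-up (EOS). Early discontinuers get one merged rule per option group. Rule C is headed "Patients who chose Early Discontinuation Option 1 or Option 2 per CTP (ITT and Full FU analysis" and, for those who complete the required study period, counts relapses "whenever they occur between the first dose of randomized treatment and the patient's EOS date". Rule D does the same for Options 3 and 4. Patients who do not complete the study period are censored at the last at-risk date, which can be a follow-up contact or an adverse event stop date. The lost-to-follow-up rule for the ITT analysis uses that date too.

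**The concern.** A programmer who follows the rules headed ITT builds a primary dataset that does not match the stated 28-week period. One who follows SAP 6.1 or 6.6 builds a different one. Three things follow from the literal reading.

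- Late discontinuers can contribute relapses and time at risk after week 28. Completers stop at the end of their treatment period.
- For these late discontinuers, Full follow-up, which is meant as a sensitivity analysis, uses largely the same time at risk as the primary analysis.
- The survival plot reads the same dataset, so its tail beyond Visit 16 rests on a handful of patients.

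There is also a gap in the ITT end date. SAP 7.4.1 fixes it only through Visit 16, which Option 3 and 4 patients do not attend. They "must have Vital Status collected approximately 28 weeks after the patient was randomised", with no window.

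**Working it through.** **1. Can EOS fall after week 28?** Visit 16 is Day 197 (protocol Flow Chart). The EOT visit is due within 7 days of last dose (protocol 6.2.2). Patients under Options 2 to 4 "will have a Follow-Up Visit performed 28 days after the EOT visit"; so do Option 1 patients who stop less than 4 weeks before Visit 16.

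| Last dose | EOT | Follow-up visit | Beyond Day 197 |
|---|---|---|---|
| Week 25 (Day 175) | Day 175 to 182 | Day 203 to 210 | 6 to 13 days |
| Week 28 (Day 196) | up to Day 203 | up to Day 231 (week 33) | up to 34 days |

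The 3-day visit window takes the latest case to Day 234, which is 37 days after Visit 16. For the protocol's own week-25 patient, rule C gives the same time for ITT and Full follow-up, where protocol 7.3 makes them differ.

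**2. The plan's own figure.** Inputs from protocol 7.7: two-sided alpha 0.05, 80% power, hazard ratio 0.5, allocation 2:1. Schoenfeld's formula gives (1.960 + 0.842)² / [(1/3)(2/3)(ln 0.5)²] = 73.5, rounded up to 74 events. This agrees with the protocol. The cap does not change it.

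**3. How many patients are affected?** Assumptions:

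- The 20% dropout is read as drug discontinuation with continued follow-up.
- Hazards are constant.
- EOS is the later of week 28 and EOT + 28 days. The visible text does not define EOS by option.

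Weekly hazards:

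- Relapse on placebo: -ln(0.70)/28 = 0.01274; half of that on active.
- Discontinuation: -ln(0.80)/28 = 0.00797.

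P(stop in weeks 24 to 28) = 0.80^(24/28) - 0.80 = 0.0259.

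Relapse-free at week 28 among those:

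- Placebo: 129 × 0.0259 × 0.70 = 2.34
- Active: 258 × 0.0259 × 0.837 = 5.59
- Total: 7.93

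**4. Extra time and relapses.** A patient stopping at week t with an EOT delay of e weeks overruns by t - 24 + e weeks. Integrating over t:

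| EOT delay | Extra patient-weeks | Extra relapses | P(at least one) = 1 - exp(-relapses) |
|---|---|---|---|
| 0 days | 15.8 | 0.13 | 12% |
| 3.5 days | 19.7 | 0.16 | 15% |
| 7 days | 23.7 | 0.19 | 18% |

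The documents do not give the timing of discontinuation. Varying its rate, with a 7-day delay:

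| Discontinuation | Patients | Extra relapses |
|---|---|---|
| 10% | 4.2 | 0.10 |
| 20% | 7.9 | 0.19 |
| 30% | 11.2 | 0.27 |
| 40% | 13.9 | 0.34 |

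**5. Effect on the test.** Simulation of 4,000 trials, N = 387, Cox model stratified by 4 countries, no loss to follow-up:

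| Scenario | HR capped | HR as written | Rejection capped | Rejection as written |
|---|---|---|---|---|
| HR 0.5, 20% discontinuation in each arm | 0.5003 | 0.5002 | 86.35% | 86.35% |
| HR 1, discontinuation 20% placebo, 40% active | 1.0025 | 1.0025 | 5.25% | 5.20% |

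In the first scenario the mean absolute change in log HR is 0.0016, and 15.4% of trials have at least one late event.

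**6. Effect on the plot.** With 2 placebo patients still at risk, one event takes the curve from 0.70 to 0.70 × 1/2 = 0.35. With 6 pooled active patients, it goes from 0.837 to 0.837 × 5/6 = 0.70.

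**The case against.** The strongest reply is that the limit is already in the same section. SAP 7.4.1 opens by placing the primary analysis on the 6.1 ITT period and defines the Visit 16 date as the end of that period, so rules C and D merely fail to repeat it. That does show the intent. But the limit is not carried into formulas expressly headed ITT, and it gives no end date for patients without a Visit 16. Planned Day 197 is in SAP Table 6.7:1 but is not linked to the ITT period.

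A second reply is that EOS may simply mean about week 28 for most discontinuers. That holds for Option 1 patients who stop more than 4 weeks before Visit 16. It cannot hold generally, because rule B uses EOS for a period that runs beyond Visit 16.

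Third, the sentence shared by protocol 7.3.1 and SAP 7.4.1, that patients who stop medication are followed to the end of the trial for the primary endpoint, may be the source of these rules. It is better read as describing how long patients are observed, since protocol 7.3 separately sets the analysis cut-off.

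Some points stand:

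- Completers dosed past Visit 16 can also add some post-week-28 time under rule A, so the contrast with completers is not absolute.
- Patients lost to follow-up will usually have a last contact before week 28.
- The placebo-curve drop is a conditional worst case: a late placebo event is expected in only about 6% to 8% of trials, and the plot shows numbers at risk.
- Recruitment stopped early (SAP 4), so the actual counts should be smaller than those at N = 387.

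**Conclusion.** The concern holds. Rules C and D, as written for the ITT analysis, contradict the 28-week period in protocol 7.3 and SAP 4, 6.1 and 6.6, and scheduled follow-up visits make the overrun real. The effect on the primary result is small: about 8 patients and 0.13 to 0.19 relapses against 74 at planning values, and at most 0.34 relapses with discontinuation up to 40%. No power loss appears, and no direction of bias in the hazard ratio can be predicted. These sizes rest on constant hazards, full follow-up of discontinuers and the EOS reading stated above. The correction is still worth making because it concerns the event and censoring dates of the primary endpoint, where the SAP should allow only one dataset.

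**What to change.** Split rules C and D into ITT and Full follow-up versions, as A and B already are.

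- **ITT:** count events and censor no later than the end of the planned 28-week period, defined once as the Visit 16 start date if that visit took place, otherwise planned Day 197. Apply the same cap wherever the last at-risk date is used, including the lost-to-follow-up rule.
- **Full follow-up:** keep EOS and the last at-risk date as they are.
- **Minor clarification in rule A:** state in the censoring bullet that last dose means treatment-period medication (EPOCH=TREATMENT1), not withdrawal/taper tablets. This keeps the protocol's provision for a patient treated for 29 weeks.

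The cost is SAP wording and one derivation line. Sample size, model and data collection do not change.

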### 7.7 DETERMINATION OF SAMPLE SIZE

Sample size considerations are given in Table 7.7: 1 based on background placebo relapse rates of 25% and 30% and for hazard reductions for the combined BI 409306 groups vs.

placebo ranging from 45% to 55%, 80% power, a two-sided alpha = 0.05, and 20% dropout after six months.

Table 7.7: 1 Trial sample sizes for selected assumptions of hazard ratios and proportions of placebo failures, with 20% dropout, 80% power, and  $\alpha=0.05$

Placebo failure rate	Hazard reduction a for BI 409306 (both groups combined) to placebo		
	55% a	50% a	45% a
30%	305	385	494
25%	372	470	603

a 55% hazard reduction is the same as a hazard ratio of 0.45; 45% hazard reduction is the same as a hazard ratio of 0.55

The sample size selected was 385 under the assumption that the relapse rate for placebo is 30% and the hazard reduction for BI 409306 is 50%. One hundred twenty-nine (129) patients will be randomised per treatment group in a 1:1:1, making the target total number of randomised patients to be 387.

Seventy-four (74) events (relapses) are needed to be observed to meet the trial objective of 80% power for the comparison of BI 409306 (N=258 for 25 mg q.d. and 50 mg q.d. combined) to placebo (N=129). This will not be an event driven trial, so the trial will end when all randomised patients have reached 6 months exposure, regardless of number of conversions observed.

Calculations were performed using ADDPLAN® 6.1.1 statistical package by [REDACTED].

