7.4.1 Primary efficacy analysis

The primary analysis will be conducted on the FAS using the ITT follow-up period as defined in Section 6.1. Because the ITT covers the 28 weeks of planned treatment and not the T/W period, the treatment arms will be pooled according to dose and disregarding the T/W randomization.

Revised CTP in Section 7.3.1:

The equality of the hazard rates will be tested by the Wald test for the treatment effect in a stratified Cox proportional hazards model at the two-sided 5% significance level. The model includes the treatment effect as the only covariate and is stratified by country. Breslow's method for handling ties will be used.

The same stratified Cox proportional hazards model will be used to estimate the hazard ratio of BI 409306 vs. placebo and the asymptotic 95% Wald confidence interval. A hazard ratio of less than one favors BI 409306. The analysis will be implemented using SAS® PROC PHREG. Cox proportional hazard model assumptions will be verified.

In early discontinued patients, if the occurance of a relapse cannot be determined between the time of discontinuation and last contact, it is assumed that no relapse has occurred. Patients who discontinue study medication will be followed until the end of the trial for the primary endpoint. Patients who are lost-to-follow up will be censored for the primary endpoint at the date of last known patient contact.

According to the CTP, we have specified more details regarding efficacy analysis using ITT FU and Full FU:

Definition of last at-risk date:

The last at-risk date determined as the latest date among: the date of first dose of study medication, the date of last drug administration, all the visit start dates (including phone contact dates in which the patient was reached and follow-up contact dates) and start or stop dates of events reported on the adverse event forms.

If a patient dies, the date of death is their last at-risk date.

Definition of Visit 16 date:

The date of Visit 16 for the determination of the ITT FU period end date will be the start date recorded on eCRF.

Time to event calculations:

A. Patients completing treatment period and study period (for ITT analysis):

Events (relapses) are counted in the ITT time to event analysis whenever they occur between the first dose of randomized treatment and the patient's Visit 16 date or the date of last dose if this occurred after visit 16. (In SDTM this is EPOCH=TREATMENT1)

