- Patients who chose Early Discontinuation Option 5, i.e. withdrew consent per CTP (for ITT and Full FU analysis): Events (relapses) are counted in the time to event analysis whenever they occur between the first dose of randomized treatment and the patient's date of consent withdrawal.
 - Patients with event counted: <date of event> <date of first drug administration> +1
 - Patients without event counted: <date of consent withdrawal> <date of first drug administration >+1 day
- Patients who are Lost-to-Follow-up (for ITT analysis): Events (relapses) are counted in the time to event analysis whenever they occur between the first dose of randomized treatment and the last at-risk date.

- Patients with event counted: <date of event> <date of first drug administration> +1 day
- Patients without event counted: <date of last at-risk> <date of first drug administration >+1 day

*Please note: Patients who are LTFU during the study (regardless of initial Early Discontinuation choice), but were successfully found towards the end of study via a vital status call, will be included in the Full-FU analysis period by replacing as follows:

• Patients without event counted: <date of vital status/date of EOS> – <date of first drug administration >+1 day

The following SAS code will be used:

```
proc phreg data= primary;
   CLASS &trt.(ref="Placebo") / order=internal;
   model aval*cnsr(1) = &trt./ties=breslow;
   strata countrdc;
   hazardratio 'HR' &trt. /diff=ref cl=both;
run;
```

Subgroup analyses will be performed on the subgroups specified in Section 6.4. Definition of Japanese patients is provided in Section 9.1. The same model as described above for the primary efficacy analysis, will be used for these analyses.

The following SAS code will be used for survival plot:

```
proc lifetest data=primary method=km plots=survival(failure test
atrisk);
time aval*cnsr(1);
id usubjid;
strata &trt. /test=logrank;
run;
```

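### The relapse subgroup analyses reuse the treatment-only primary Cox model, so the visible SAP text gives a result per subgroup level but no estimate of whether the effect differs between levels

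*SAP*

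**What the plan says.** SAP Section 7.4.1 introduces the subgroups with "Subgroup analyses will be performed on the subgroups specified in Section 6.4", points to Section 9.1 for the definition of Japanese patients, and sets the method: "The same model as described above for the primary efficacy analysis, will be used for these analyses". The primary model is described in the same section: "The model includes the treatment effect as the only covariate and is stratified by country". The PHREG code agrees. Its model statement is "model aval*cnsr(1) = &trt./ties=breslow", with country in the strata statement and confidence limits requested for the hazard ratio. No subgroup or treatment-by-subgroup term appears.

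The only visible heterogeneity analysis is in SAP Section 7.5.1. It is a descriptive p-value for treatment by country from the MMRM, and it concerns the PANSS positive score, not relapse. Sections 6.4 and 9.1 are not in the public text.

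**The concern.** A subgroup analysis is normally read to learn whether the treatment effect varies between patients. A treatment-only model fitted separately in each level does not estimate that. It gives two or more hazard ratios, each with its own p-value against no effect, and leaves the comparison to the reader's eye. The common shortcut is to take significance in one level and non-significance in another as evidence of a difference. That is unreliable because each level holds only part of the events: with a true effect of the planned size, power within a level is moderate, and discordant p-values are then an ordinary result of chance. The risk is a mistaken impression that the drug works in one kind of patient and not in another. The primary, individual-dose and key secondary conclusions are not affected.

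**Working it through.** **Inputs.** Protocol Section 7.7 gives two-sided alpha 0.05, 80% power, a 30% placebo relapse rate and a 50% hazard reduction (hazard ratio 0.50). It also states "Seventy-four (74) events (relapses) are needed to be observed to meet the trial objective of 80% power", with 258 patients on active treatment and 129 on placebo. The placebo share is 1/3, so the information per event is (1/3)(2/3) = 2/9. SAP Section 4 says recruitment stopped early but gives no achieved number of patients or events; lower event counts below are assumptions. Subgroup sizes are also assumptions, because Section 6.4 is not visible.

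**Reproducing the plan's figure.** Schoenfeld events = (1.960 + 0.842)² / [(2/9)(ln 2)²] = 73.5, rounded up to 74, as stated. Power at 74 events is 80.3%.

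**Power within a level.** With d events in the level, power = Φ(√(d × 2/9) × ln(1/HR) − 1.96). For two equal halves, d = 37: √8.222 × 0.693 − 1.96 = 0.028, so power is 51.1%.

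**Chance that exactly one level is significant when the effect is the same in both.** P = p₁(1 − p₂) + p₂(1 − p₁). For equal halves, 2 × 0.511 × 0.489 = 50.0%. Both are significant in 26.1% of trials and neither in 23.9%. Among trials with a significant pooled result the discordance is 57%.

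**Sensitivity.**

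| Change from the base case (74 events, HR 0.50, equal halves) | Exactly one level significant |
|---|---|
| HR 0.45 / 0.55 (planned range) | 47% / 48% |
| HR 0.6 / 0.7 / 0.8 | 43% / 29% / 17% |
| 60 / 50 / 35 events (assumed) | 49% / 47% / 40% |
| 70:30 split (power 65% and 34%) | 55% |
| 80:20 split (power 71% and 24%) | 61% |

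**Simulation check.** Patient-level Cox simulation used 4,000 runs per size, exponential relapse and 20% dropout, equal halves on average and no country strata. Discordance was 48.9% at N = 387 (about 73 events), 50% at N = 300 (about 56 events), 47% at N = 260 (about 49 events) and 45% at N = 200 (about 38 events). In the same runs a two-sided 5% test of the difference between the two log hazard ratios rejected in 4.0% to 5.1% of trials.

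**What an interaction test can detect.** With 37 events per half, the standard error of the log ratio of hazard ratios is √(2 / (37 × 2/9)) = 0.493. Power for a two-fold ratio is Φ(0.693/0.493 − 1.96) = 29%. For 80% power the ratio must be exp(2.80 × 0.493), about 4.0.

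**The case against.** The strongest objection is that part of the plan is withheld. The contents list goes from Section 6.3 to 6.5, and the missing Section 6.4 could contain an interaction test, a descriptive-only rule or minimum subgroup sizes. Naming a model for subgroup hazard ratios does not exclude a separate interaction analysis. This stands, and it makes the point conditional. It does not remove it, because Section 7.4.1 is where the method is set, and its wording and code are explicit.

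Three stronger readings are tempting and are not supported:

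- A reader might infer that subgroup results will drive the fast-track decision and phase III preparation mentioned in SAP Section 4. That section does not mention subgroups or Japanese patients, and the details in Section 9.2 are not public.
- A reader might infer that the sponsor intends to label subgroups as positive or negative. No visible passage does so, and no subgroup is in the testing hierarchy. The error arises only if someone compares the per-level p-values.
- A reader might take the 50% as a general property of this trial. It needs a true hazard ratio of 0.50, equal halves and 74 events, an event target that the early stop of recruitment has put in doubt. With no effect at all, discordance in either direction is only 2 × 0.05 × 0.95 = 9.5%.

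It is also fair to say that the interaction test is weak, and that an approximate ratio of hazard ratios could be worked out from the confidence limits the code already requests. Both stand. They argue for reporting the ratio with its interval in advance and not leaning on the interaction p-value; they do not argue for leaving the comparison to each reader.

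**Conclusion.** The point holds as a low-cost improvement, on condition that Section 6.4 does not already provide an interaction analysis. As far as the visible text goes, the relapse subgroups get separate hazard ratios, confidence intervals and p-values and no estimate of effect modification, while the PANSS endpoint does get a descriptive heterogeneity test.

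If the separate p-values were compared, a common effect would look discordant in about half of trials under the design assumptions with two equal subgroups. The figure falls to about 40% to 49% with an assumed 35 to 60 events, falls further for effects weaker than planned, and rises for unequal subgroups. The corresponding error rate of an interaction test is about 5%. These figures ignore any loss of information from country stratification within small subgroups. Nothing in the formal hypothesis testing changes.

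**What to change.** If Section 6.4 has no interaction analysis, replace the model sentence in SAP Section 7.4.1 with text along these lines:

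*For each subgroup factor, one Cox model stratified by country is fitted on the FAS over the ITT follow-up period, with treatment, subgroup and treatment-by-subgroup terms. Where the factor is fully determined by country, the subgroup main effect is omitted because the strata absorb it. Subgroup hazard ratios with 95% CI, the ratio of hazard ratios with 95% CI and a descriptive interaction p-value are reported. No statement of significance is made within a subgroup.*

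Japanese versus non-Japanese should be handled as one such factor. The exception for country applies if the Section 9.1 definition means the country Japan, which is one of the countries listed in SAP Section 5.4.1.

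The cost is one paragraph and one added model term, with no new data and no effect on the primary test or its alpha. The downside is low power: at 74 events in equal halves the interaction test reaches 80% only for a ratio of hazard ratios of about 4, and fewer events make this worse. That should be stated beside the result, so that a non-significant interaction is not read as proof of a uniform effect.
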